## 8.2 Primary outcome statistics

The primary objective for this pilot study wound healed status at week 12. For non-inferiority analysis, patients who withdraw prior to completion of the study or do not attend week 12 appointment will be assigned the worst-case healing outcome (not healed at week 12).

The test for non-inferiority concerns the proportion of patients attaining ulcer closure by week 12 for both treatment groups, and the associated 97.5% one-sided confidence interval for the difference. Non-inferiority of Andoflex is considered valid if the lower limit of the 95% confidence interval for the difference between treatment means (Andoflex – Coban2) is not more negative than -15%. That is, non-inferiority for Andoflex is demonstrated when a maximum of 15% fewer patients using this bandage, compared with patients using Coban2, have healed by week 12 of treatment. This approach was taken in previous non-inferiority trials for ulcers (Harding et al, 2012; Moffatt et al, 2019), and is outlined in papers by Oczkowski (2014) and Flight (2016).

For comparative performance (superiority) analysis, any statistically significant difference (p-value < 0.05) between the two treatment arms will be determined with Chi-squared test. This will be done since Dunn et al postulate that non-inferiority and superiority trials effectively aim to answer the same hypothesis (Dunn et al, 2018)

Analysis will be performed on a per protocol and also an intention to treat basis. Multiple imputation (default five imputations) will be applied for missing values for the outcome measures, and inferential statistics will be performed on pooled data. Data will first be collated in Microsoft Excel, followed by analyses performed using SPSS v20.

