Patient population	
 
Pragmatic approach to allow inclusion of wider cohort of patients than those with pure venous leg ulcers (VLU).
 
Therefore, patients with leg ulcer who are suitable for reduced (ie 'Lite') compression are considered for inclusion.
 
Specifically, these are: 
 
VLU
 
Mixed venous and arterial leg ulcers
 
 
 
Suitability for reduced compression is an ABPI of 0.5 -0.8 depending on holistic assessment. ABPI measured within last 3 months is part of the decision making to use reduced (Lite) rather than full compression. Only if ABPI or other diagnostic method (eg pulse palpation and ultrasound diagnostics, toe pressure assessment or arterial imaging) is not available or applicable then provision of solely a clinical assessment is allowed.
 

Sample size	
 
A total of 92 participants, over the age of eighteen, with leg ulcers. Power beta of 80%, one-sided alpha p-value of 0.025, non-inferiority limit 15%. Assumption of 15% difference in absolute percentage healed ulcers in intervention (Andoflex) arm versus control (Coban2) arm.
 
Therefore, 97.5% confidence interval for Andoflex to be no more than 15% worse than mean ulcers healed percentage for Coban2.
 
Sample size with 10% attrition rate included: 92 patients Of which: 
 
46 Patients to receive Andoflex TLC Calamine Lite
 
46 Patients to receive Coban2 Lite
 
 
 
Participants must have the capacity to provide informed written consent and complete patient reported outcome measures. Participants are recruited from the local community nursing caseload and identified in hospital clinics.
 

	Randomisation will be stratified for ulcer size, with cut-off	
	PUSH score of up to and including 10, or 11 and above.	
Sponsor	North Cumbria Integrated Care NHS Foundation Trust	
5001301	North Cumbra integrated care with roundation must	
Manufacturer & funder	Milliken Healthcare Inc	
	UK-based contact: [name], Clinical Specialist EMEA ,	
	Milliken Healthcare Division, [name] ,	
	[contact]	
Chief Investigator	[name], vascular specialist nurse, Vascular Surgery	
	Dept, North Cumbria University Hospitals NHS Trust.	
	[contact]	
Co-investigators	[name] PhD, Research Project Lead, [contact];	
	Cumbria Partnership NHS Foundation Trust	
	R&D Department, Carleton Clinic	
	[name]	
	[contact]	
	[name], GPwSI Research, Cumbria Partnership NHS	

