#### 6. SUBJECTS

#### 6.1 Anticipated number of research subjects

Locally, we have healing data available from two previous trials involving venous leg ulcers, namely the PREVUE and APRICOT trials (Jonker et al 2020a, and Jonker et al 2020b). One caveat is that those

studies concerned pure venous leg ulcers and that compression bandaging could be full (40 to 50mmHg) or Lite (20 to 30 mmHg). Nonetheless, from these studies we know that the study followup time points are valid and APRICOT compared Andoflex vs Coban2.

Below a summary is given for the sample size needed. The primary outcome, wound status (healed vs non-healed) is used for sample size calculation. The non-inferiority related sample size calculation has been performed using the calculator at https://www.sealedenvelope.com/power/binary-noninferior/. Power calculations for sample size assume 80% power and 2.5% one-sided confidence interval. The non-inferiority limit is set at 15% in favour of the Coban2 control bandage. The result is shown in Table 4. Since some patients may withdraw over the course of the 12-week trial period, a 10% dropout rate is calculated into the sample size. A 1:1 allocation to the two types of compression bandage will be applied.

	Sample size calculation	
	Intervention Bandage (Andoflex)	Control Bandage (Coban2)
Ulcer healed	65%	50%
Ulcer not healed	35%	50%
	Sample size required without any du Sample size with 10% attrition rate Total of 92 patients: - 46 Patients to receive Ando - 46 Patients to receive Coba	flex

Table 4, Sample size calculations

The CONSORT guidelines require a statement on the number of patients assessed for eligibility (Schulz, Altman & Moher 2010). The number of patients screened but who did not meet the inclusion criteria or who declined to participate will be recorded, as will any patients who are lot to follow-up (Appendix 5).

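### Section 8.2 paraphrases its confidence-limit rule for non-inferiority as a rule on the observed difference, which is far weaker; the paraphrase should be deleted or reworded

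*Protocol*

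**What the plan says.** Section 8.2 introduces the non-inferiority test as a comparison of the proportions healed by week 12, with a one-sided 97.5% confidence interval for the difference. It then gives the criterion: "Non-inferiority of Andoflex is considered valid if the lower limit of the 95% confidence interval" for Andoflex minus Coban2 does not fall below -15%.

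The sentence after that opens with *That is* and says, of healing at the 12-week point: "non-inferiority for Andoflex is demonstrated when a maximum of 15% fewer patients using this bandage, compared with patients using Coban2, have healed".

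The rest of the protocol goes with the first statement. The summary gives "one-sided alpha p-value of 0.025, non-inferiority limit 15"%. Section 6.1 says "Power calculations for sample size assume 80% power and 2.5% one-sided confidence interval" and "The non-inferiority limit is set at 15% in favour of the Coban2 control bandage". Table 4 assumes 65% healed on Andoflex and 50% on Coban2, and arrives at 92 patients, 46 per arm.

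**The concern.** The second sentence is meant to explain the first, but it drops the confidence limit. It speaks of patients who have healed, which are observed counts, and says that non-inferiority is thereby demonstrated. Taken at face value, any observed shortfall of up to 15 points would be enough.

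The two statements are not equivalent. A confidence-limit rule asks whether the data rule out a true deficit larger than the margin. A rule on the observed difference asks only whether the estimate falls on the right side of the margin, and a bandage lying exactly on the margin passes that about half the time.

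What is at stake is the sentence that a report would quote for the primary conclusion. Someone facing an observed deficit of, say, 5 points could cite the protocol in support of a non-inferiority claim that its own test would reject. Correcting the sentence after the data are seen would look data-driven.

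**Working it through.** **Inputs.** Margin 15 percentage points, one-sided alpha 0.025 and 80% power (summary, section 6.1). Healing 65% v 50%, 1:1 allocation, 10% attrition, 46 per arm (Table 4, section 6.1). Patients who withdraw or miss week 12 count as not healed in the non-inferiority analysis (section 8.2), so 46 per arm stay in the denominator. Assumption: a Wald interval, since the protocol names no interval method.

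**Step 1: reproduce the sample size.**

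n per arm = [0.65 × 0.35 + 0.50 × 0.50] × (1.960 + 0.842)² / (0.15 + 0.15)² = 0.4775 × 7.849 / 0.09 = 41.6, so 42 per arm and 84 in total. Adding 10%: 84 × 1.1 = 92.4, in agreement with 92. The size therefore rests on a one-sided 2.5% confidence-limit test.

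**Step 2: locate the two thresholds, with Coban2 at 23/46 (50%).**

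95% limits = d ± 1.96 × √[p_A(1 − p_A)/46 + p_C(1 − p_C)/46].

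- 16/46 on Andoflex: d = -15.2 points. Fails both rules.
- 17/46: d = -13.0 points, SE = √(0.005065 + 0.005435) = 0.1025, limits -33.1 to +7.0. Passes the paraphrase, fails the confidence-limit rule.
- 25/46: d = +4.3 points, lower limit -16.0. Passes the paraphrase, fails the confidence-limit rule.
- 26/46: d = +6.5 points, SE = √(0.005342 + 0.005435) = 0.1038, lower limit -13.8. Passes both.

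Every result from 17 to 25 healed on Andoflex gets opposite verdicts. The thresholds are 6.5 − (−13.0) = 19.5 points apart.

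**Step 3: probability of declaring non-inferiority.** Exact enumeration of two independent binomial arms of 46, Coban2 at 50%. The paraphrase passes if d ≥ -15%; the confidence-limit rule passes if the lower limit ≥ -15%.

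| True difference | Paraphrase as written | Confidence-limit rule |
|---|---|---|
| -25 points | 13% | 0.1% |
| -20 points | 27.7% | 0.6% |
| -15 points (the margin) | 46.4% | 2.4% |
| 0 | 91% | 30% |
| +15 points (design) | 99.8% | 83% |

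At true equality the two sentences would disagree in about 91 − 30 = 61% of trials, so the gap covers ordinary results.

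**Step 4: sensitivity.** For Coban2 rates of 40% to 70% and 41 to 47 per arm, at a true deficit of 15 points, the paraphrase passes 46% to 54% of the time and the confidence-limit rule 2.4% to 2.7%. The spread around one half comes from whole patients: with 46 per arm, 0.15 × 46 = 6.9, so the largest shortfall allowed is 6 patients. If a 15% reduction is read as relative, the pass rate at 35% v 50% is about 22%, still far above 2.5%. Section 8.2 sets the margin on the difference scale, so the absolute reading is the natural one.

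**The case against.** The strongest objection is that the operative rule is not in real doubt. Section 8.2 names the one-sided 97.5% interval and then the lower-limit criterion before the disputed sentence. The summary and section 6.1 tie the 15% limit to a one-sided 2.5% level, and the sample size follows from that rule. The opening *That is* marks a plain-language gloss, not a second criterion. On this view, the 46% and 28% pass rates arise only if an analyst ignores every other statement of the rule.

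This largely stands. A reader might infer that the protocol leaves two rules equally open, or that the weaker one will be applied; the text supports neither. What remains is that the gloss is wrong as written, at the place where the primary conclusion is defined.

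Two further readings are tempting and should not be added:

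- The summary also says "97.5% confidence interval for Andoflex to be no more than 15% worse than mean ulcers healed percentage for Coban2", which a reader might take as a two-sided 97.5% interval and so a third, stricter rule. The same summary entry gives a one-sided alpha of 0.025, and section 8.2 calls the 97.5% interval one-sided. That is the same test as the lower limit of a two-sided 95% interval, so the two wordings agree.
- Section 8.2 says "Analysis will be performed on a per protocol and also an intention to treat basis" without saying which analysis decides. A reader might count this as a gap in the rule. It is commonly settled in the statistical analysis plan, which is not at hand. Requiring success in both populations would be a new decision rule, not a correction of this sentence.

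**Conclusion.** The point holds as an incorrect paraphrase of a correct rule. Followed literally, it would raise the chance of a false non-inferiority claim at the margin from about 2.4% to about 46%, and would move the pass mark against 23/46 from 26/46 down to 17/46. These figures assume 46 analysed per arm, Wald limits and a 50% Coban2 healing rate; the result at the margin changes little over the ranges in step 4.

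They measure how far the sentence is from the intended rule. They are not a forecast of the trial's error rate, because the confidence-limit rule is evidently the one meant. The design, margin and sample size are not called into question by this point. The edit is small, but it governs the primary conclusion and should be made before analysis.

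**What to change.** In section 8.2, keep the lower-limit criterion and delete the sentence that opens with *That is*. If a plain-language gloss is wanted, replace it with:

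> That is, non-inferiority is demonstrated only when the data exclude, with one-sided 97.5% confidence, a true healing proportion on Andoflex more than 15 percentage points below Coban2.

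The replacement keeps the existing boundary (a lower limit of exactly -15% still passes), and writing percentage points removes the relative reading. The cost is wording only: no change to sample size, margin, alpha or data collection.

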## 6.1.1 Randomisation and Blinding

Following written consent patients will be allocated at random to the one of two treatment arms, using a non-restricted randomised sequence generated for the whole sample using a free ware randomisation programme, see https://www.sealedenvelope.com/. The randomisation will be stratified by ulcer size, with one group being those with a PUSH score of up to and including 10, or a PUSH score of 11 or higher.

Each next randomisation allocation will be obtained from the sealedenvelope.com account for this PEACH trial. The randomisation will be stratified by ulcer size, with one group being those with a PUSH score of up to and including 10 (LOW PUSH randomisation), or a PUSH score of 11 or higher (HIGH PUSH RANDOMISATION).

Each next randomisation allocation will be obtained from either the LOW PUSH or HIGH PUSH the sealedenvelope.com account for this PEACH trial. The PUSH score is done as part of standard clinical practice and is a swift method (appr. 1 minute to obtain).

Since it will not be known up front how many patients will be LOW PUSH or HIGH PUSH, a total of 60 randomisations will be generated for each stratification, in blocks of 10 randomisations within said stratification. This means 6x10 randomisations for LOW PUSH and also 6x10 randomisations for HIGH PUSH. If one of the stratifications reaches 60 then only the other stratification can be recruited into going forward. It is recognised that random selection does not guarantee representativeness but variables which may affect the outcome variable are more likely to be balanced out and reliability enhanced (Thomas 1990).

As the study involves different looking bandages, it is not possible to achieve blinding for the participants. However, statistical analysis is carried out blinded to group allocation, by persons who have not had contact with study participants.

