## 8.3 Secondary outcome statistics

To evaluate the effect of the different reduced compression bandages on leg ulcer healing, data from the two treatment arms will be compared.

Ulcer healing and more general health measures is assessed by the following parameters:

- Ulcer status (healed vs non-healed)
- Ulcer size (cm^2, measured with wound grid)
- PUSH score
- Visual analogue pain score
- Visual analogue pruritus score
- VEINES-QoL
- EQ-5D-5L

To assess the Ulcer size, PUSH score, visual analogue pain score, and visual analogue pruritus score, which are measured every 6 weeks, per treatment arm the average difference between time points will be calculated per treatment group (Wilcoxon test). To compare between the groups, Mann-Whitney U-test will be applied.

To measure patient-reported outcome measures on quality of life (VEINES-QoL and EQ-5D-5L) at baseline, week6 and week 12; the Wilcoxon test will be applied within treatment arms (over time) whereas the Mann-Whitney U-test will be performed between treatment arms. Data of the two treatment arms will be compared by applying the Mann-Whitney U-test.

Subject to sufficient data being available, Cox proportional hazards regression analysis will be conducted to investigate the role of the compression bandage itself and other covariates in leg ulcer healing rates. Other covariates include: leg ulcer size and chronicity at baseline, patient age, ulcer aetiology (pure venous vs other), absence/presence of co-morbidities, ulcer location, history of recurrent ulcers.

The following descriptive statistics will be reported on where possible:

- Number of patients screened
- Number of patients eligible/ineligible, and percentage of patients consented into the trial
- Number of patients completed the trial/discontinued (plus reasons if discontinued)

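### Randomisation is stratified by PUSH score but section 8.2 analyses without the strata; if PUSH predicts healing, some precision is given up for no benefit

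*Protocol*

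**What the plan says.** **Allocation.** Protocol section 6.1.1: "The randomisation will be stratified by ulcer size, with one group being those with a PUSH score of up to and including 10", the other group having 11 or more. The lists are generated "in blocks of 10 randomisations within said stratification". The protocol summary and section 5.3 repeat the stratification.

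**Non-inferiority.** Section 8.2 compares the proportion healed by week 12 in the two arms, with "the associated 97.5% one-sided confidence interval for the difference". The rule is that "the lower limit of the 95% confidence interval for the difference between treatment means (Andoflex – Coban2) is not more negative than -15" per cent. No interval method and no strata are named.

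**Superiority.** Section 8.2: any significant difference "between the two treatment arms will be determined with Chi-squared test". No strata are named.

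**Covariates.** Baseline size enters only the secondary Cox model in section 8.3, which is run if there are enough data: "Other covariates include: leg ulcer size and chronicity at baseline, patient age, ulcer aetiology" and others.

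**Sample size.** Section 6.1: "Power calculations for sample size assume 80% power and 2.5% one-sided confidence interval" and "The non-inferiority limit is set at 15% in favour of the Coban2 control bandage". Table 4 assumes 65% healed on Andoflex and 50% on Coban2. The total is 92, including 10% attrition.

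**The concern.** Blocking within strata forces near-equal numbers per arm in each PUSH group. Chance imbalance in PUSH therefore contributes almost nothing to the treatment difference. An unstratified standard error still counts the between-stratum variation as noise. If the strata heal at different rates, that standard error is too large: the interval compared with -15% is too wide, and the Chi-squared test rejects less often than its nominal level allows.

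At stake is efficiency in a small trial. The sponsor has already gone to the trouble of stratifying, and the benefit to precision is collected only if the analysis uses the strata.

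**Working it through.** **1. Reproduce the plan's sample size.** Inputs from section 6.1: rates 0.65 and 0.50, margin 0.15, one-sided alpha 0.025, power 80%.

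Variance sum = 0.65×0.35 + 0.50×0.50 = 0.2275 + 0.25 = 0.4775.

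n per arm = (1.960 + 0.842)² × 0.4775 / (0.15 + 0.15)² = 7.849 × 0.4775 / 0.09 = 41.64, so 42 per arm and 84 in total.

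For attrition, 83.3 / 0.9 = 92.5 and 83.3 × 1.1 = 91.6. The stated 92 is reproduced, and it comes from an unstratified formula.

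**2. Standard error with and without strata.** Assumptions, not in the protocol: half the patients in each stratum, and the same LOW-minus-HIGH gap g in both arms. The within-stratum variance in each arm is p(1-p) - g²/4, so the sum over two arms is 0.4775 - g²/2.

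| Gap g | Variance sum | SE ratio to unstratified | Half-width at 42 per arm | SE at 46 per arm |
|---|---|---|---|---|
| 0 | 0.4775 | 1.000 | 20.9 points | 0.102 |
| 20 points | 0.4575 | 0.979 | 20.5 | 0.100 |
| 30 points | 0.4325 | 0.952 | 19.9 | 0.097 |
| 40 points | 0.3975 | 0.912 | 19.1 | 0.093 |

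Half-width = 1.96 × √(variance sum / 42); the last column is √(variance sum / 46). With a 30/70 split the ratio is 0.982 at 20 points and 0.927 at 40, so the gain is slightly smaller.

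**3. Non-inferiority power at 65% v 50%.** Analytically, the unstratified test with no gap at 42 per arm has power Φ(0.30/0.1066 - 1.96) = Φ(0.853) = 80.3%.

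Simulation used blocks of 10 within two equal strata, with 20,000 runs per row at 84 patients and 12,000 at 92. The stratified estimate was D = Σw_k d_k / Σw_k, with w_k = n_1k n_0k / (n_1k + n_0k) and variances p(1-p)/(n-1) in each stratum and arm. The 92-patient rows matter because section 8.2 counts withdrawals as not healed, which keeps them in the denominator.

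| Patients | Gap | Unstratified | Stratified |
|---|---|---|---|
| 84 | 0 | 80.6% | 80.3% |
| 84 | 20 | 80.9% | 81.3% |
| 84 | 30 | 81.3% | 83.1% |
| 84 | 40 | 82.7% | 86.3% |
| 92 | 0 | 83.5% | 83.3% |
| 92 | 20 | 83.8% | 84.4% |
| 92 | 40 | 84.8% | 89.1% |

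**4. One-sided error at the margin (50% v 35%, nominal 2.5%).** At 84 patients and gaps of 0, 20, 30 and 40, the unstratified interval gives 2.6%, 2.3%, 2.2% and 1.8%. The stratified interval with n-1 variances stays between 2.4% and 2.6%. At a 40-point gap the unstratified figure is about 1.5 to 1.8% across the 84- and 92-patient runs. A stratified Wald interval with plug-in variances at 92 patients ran at up to about 3%.

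**5. Superiority at 84 patients.** Chi-squared power is 29.8%, 29.2%, 28.5% and 28.3% at the four gaps. The stratified statistic gives 30.6%, 30.9%, 31.9% and 34.4%. That statistic was a stratified Wald test standing in for Cochran-Mantel-Haenszel, and its two-sided error was 5.4 to 5.9%, so part of this gain is not real.

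**The case against.** **The loss is conditional.** A reader might infer that power is certainly lost. The protocol reports no healing rates by PUSH stratum, so the gaps above are assumptions. At zero gap nothing is lost, and at 20 points the effect is close to negligible. This objection stands and limits the claim.

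**The trial is not underpowered for this reason.** The sample size was computed without strata, and the unstratified analysis reaches the planned 80% on the protocol's assumed rates. Power is forgone relative to a better analysis; it does not fall short of the plan. The error is also in the safe direction, since a conservative interval does not produce extra false claims of non-inferiority. Both points stand.

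**The Chi-squared test is not the primary decision.** It belongs to the superiority comparison. For the deciding interval, section 8.2 names no method, and a statistical analysis plan not shown here could specify a stratified one. This stands in part. Section 8.2 does describe a simple difference between whole-arm proportions and fixes the Chi-squared test outright, so a later plan that used the strata would have to depart from that test.

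**A stratified interval can be slightly liberal.** This is true of the plug-in Wald form, as step 4 shows. It bears on the choice of interval and is no reason to ignore the strata.

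**PUSH is not ulcer size.** On the Appendix 1 scoring, an 8.0 cm² granulating ulcer with light exudate scores 7+1+2 = 10, while a 3.0 cm² sloughy ulcer with heavy exudate scores 5+3+3 = 11. A reader might conclude that the stratification is faulty. Section 5.3 presents PUSH as a measure of severity and healing, so this shows a loose label and no analysis error.

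**Conclusion.** The point holds as a conditional matter of efficiency. The design stratifies and blocks on PUSH; the stated analysis does not use the strata. If PUSH predicts healing, the unstratified interval is wider than necessary and the test is conservative.

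With equal strata, a common gap in both arms, 65% v 50% healing and 84 to 92 patients, the cost is:

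- gap 0: nil;
- gap 20 points: about 2% in standard error and 0.5 to 1 point of non-inferiority power;
- gap 40 points: about 8 to 9% in standard error and about 4 points of power.

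The protocol does not support saying that the primary result would be biased, that type I error is inflated, or that this choice takes power below 80%. The case for change is that the improvement is free, and that it must be fixed in advance: a choice between adjusted and unadjusted results made after seeing a lower limit near -15% would be open to challenge.

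**What to change.** In section 8.2:

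- Define the interval compared with -15% as that of the PUSH-stratified risk difference with Mantel-Haenszel weights. Use a stratified score interval or within-stratum variances with n-1 denominators, not the plug-in Wald form.
- Replace the Chi-squared test with the Cochran-Mantel-Haenszel test over the two PUSH strata.
- Keep the unstratified difference and Chi-squared test as a sensitivity analysis.

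Further adjustment for measured ulcer area and chronicity is optional.

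The cost is wording only. PUSH is scored before allocation, and area and chronicity are already collected at baseline. The sample size need not change. The wording should be settled before outcomes are examined by arm.

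### Five imputations, the software default fixed in section 8.2, leave avoidable random-seed noise in the superiority test and in other results that use imputed data

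*Protocol*

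**What the plan says.** Protocol section 8.2 contains two missing-data rules.

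- **Non-inferiority analysis.** For this analysis, "patients who withdraw prior to completion of the study or do not attend week 12 appointment will be assigned the worst-case healing outcome", that is, not healed at week 12. Non-inferiority is accepted if the "lower limit of the 95% confidence interval for the difference between treatment means (Andoflex – Coban2) is not more negative than -15" per cent.
- **Imputation.** Later in the section, after the superiority paragraph and the sentence on per-protocol and intention-to-treat analyses: "Multiple imputation (default five imputations) will be applied for missing values for the outcome measures", and "inferential statistics will be performed on pooled data". The sentence does not list the outcomes or analyses that it covers.

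The superiority comparison of healing (Chi-squared test, p < 0.05) has no worst-case rule of its own, so the imputation sentence is the only one that reaches it. On the expected amount of missing data, section 6.1 says only that "a 10% dropout rate is calculated into the sample size".

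**The concern.** Multiple imputation fills each missing value with random draws. With few imputations, the pooled difference, its standard error and the reference degrees of freedom all vary with the seed. With about 5 of 46 binary outcomes missing per arm, five rounds of draws do not average this out. If the result lies near p = 0.05, the same dataset can be reported as significant or not depending on a seed that the protocol does not ask anyone to fix or record.

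The number five is set in the protocol itself, so this is not a detail that the protocol leaves to an analysis plan.

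**Working it through.** **Inputs.** From section 6.1: 46 patients per arm, healing 65% (Andoflex) v 50% (Coban2), 10% dropout, one-sided 2.5%, power 80%, margin 15 points. From section 8.2: m = 5 imputations. Assumed, because the protocol does not say: outcomes missing at random within arm, equal missing shares in both arms, and an imputation model without covariates.

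**Step 1. The plan's own sample size.** n per arm = (1.960 + 0.842)² × (0.65×0.35 + 0.50×0.50) / (0.15 + 0.15)² = 41.6, so 42 per arm and 84 in total. Adding 10% gives 84 × 1.1 = 92.4, which agrees with the planned 92.

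**Step 2. Noise in the pooled difference.** With n = 46 and k = 4.6 missing per arm, the between-imputation variance is the sum over arms of [k p(1−p) + k² p(1−p)/(n−k)] / n².

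- p = 0.65: (1.0465 + 0.1163)/2116 = 0.00055
- p = 0.50: (1.1500 + 0.1278)/2116 = 0.00060
- Sum: B = 0.00115

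The seed-to-seed SD of the pooled difference is √(B/m): 1.5 points at m = 5 and 0.48 points at m = 50.

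**Step 3. Effect on the superiority decision.** Simulation: for each missing binary outcome, a draw from the Beta posterior within arm and then a Bernoulli draw; Rubin's rules with a t reference; a pooled Wald test standing in for the Chi-squared test; two seeds per simulated trial at 65% v 50%.

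| Missing per arm | m | Trials in which two seeds disagree on p < 0.05 |
|---|---|---|
| 5 of 46 | 5 | about 6% |
| 5 of 46 | 50 | about 1% |
| 9 of 46 | 5 | 8–9% |
| 9 of 46 | 50 | about 3% |

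Two fixed datasets, each with 5 of 46 missing per arm:

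- Observed 28/41 v 19/41 healed: about 65% of seeds give p < 0.05 at m = 5 (central 95% of p-values 0.017 to 0.094), about 95% at m = 50 and about 99% at m = 100.
- Observed 28/41 v 20/41 healed: about 19% of seeds are significant at m = 5, and under 1% at m = 50.

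**Step 4. The -15% decision.** Under the worst-case rule, withdrawals and non-attenders receive a fixed value, so they add no seed variation. For example, 23/46 v 20/46 always gives a lower limit of -13.8 (pass), and 22/46 v 20/46 always gives -16.0 (fail).

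If imputed healing were used in this test instead, with 5 of 46 missing per arm, the seed SD of the lower limit would be about 2.0 points at m = 5, 0.9 at m = 20 and 0.6 at m = 50. Observed 23/41 v 20/41 would then pass with 60% of seeds at m = 5. Observed rates close to the design's 65% v 50% would pass with every seed (mean lower limit -4.4), and 50% v 50% with none.

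**The case against.** A reader might infer that the non-inferiority verdict itself depends on the seed, since 2 points of noise sits beside a 15-point margin. The documents do not support this. The 10% dropout consists of the patients whom section 8.2 counts as not healed in that analysis. Under that rule, imputation is left only for someone who attends week 12 without a recorded wound status, which should be rare because status is a scheduled week 12 observation. The imputation sentence carries no explicit exemption for week 12 healing, so an analyst could apply it to the margin test. That would override a rule written specifically for that test.

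Four other objections carry weight.

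- **Flips need a result near the threshold.** True. The 6% is an average over simulated trials, most of which are not close.
- **The imputation model could be better.** True. Week 6 status and baseline ulcer size are collected, and using week 6 status would lower the noise.
- **Little precision is lost.** True. The within-imputation variance is about (0.65×0.35 + 0.50×0.50)/46 = 0.0104. The total is 0.0104 + 1.2×0.00115 = 0.0118 at m = 5, against 0.0115 with unlimited imputations, so the standard error rises by about 1%. The issue is reproducibility of a decision, not power.
- **Fifty is not a sharp requirement.** Also true. Twenty imputations already remove much of the noise. Fifty is proposed because it costs almost nothing more.

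None of this gives a reason to keep five.

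**Conclusion.** The point holds as a cheap improvement to the analyses that use imputed data: mainly the superiority comparison of healing, and also week 6 status and the other secondary outcomes. At the plan's own healing rates and about 10% missing, two seeds disagree on superiority in about 6% of trials with five imputations, against about 1% with 50. These figures rest on data missing at random within arm, equal missingness in both arms, no covariates in the imputation model and a Wald test in place of the Chi-squared test. No disagreement rate was calculated for the secondary outcomes, so for them the argument is one of principle.

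The -15% decision is outside the point as long as the worst-case rule is followed. It would become seed-dependent, with an SD of about 2 points in the lower limit, only if imputed healing were used in that test.

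**What to change.** In section 8.2, replace the parenthesis that sets the default of five with: at least 50 imputations, with the random seed fixed and recorded before unblinding. Add that this applies to the analyses other than the worst-case non-inferiority analysis. The addition matters because raising the number alone would leave open whether imputation may enter the margin test.

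The cost is one line of text and slightly more computing time. No patients, visits or data items change.
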